8.3.3.3 EXPECTEDNESS

The IMSM is typically responsible for determining whether an SAE is **expected** or **unexpected**. An SAE is considered unexpected if the nature, severity, or frequency of the event is not consistent with the risk information previously described for the study treatment or based on the underlying disease.

8.3.4 TIME PERIOD AND FREQUENCY FOR EVENT ASSESSMENT AND FOLLOW-UP

The occurrence of an adverse event (AE) or serious adverse event (SAE) may come to the attention of study personnel during study visits and interviews of a study participant presenting for medical care, or upon review by a study monitor. The following AEs will be reported in the study database: 1) Any serious AE (SAE) possibly related to study participation occurring from the Baseline assessment through the participant’s end of study; 2) Any AE occurring from the Baseline Assessment through the participant’s end of study that has a reasonable possibility of being related to study participation. All such events are captured on the appropriate CRF and entered into WebDCU™. Information to be collected for reportable adverse events includes event description, time of onset, clinician’s assessment of severity, relationship to study product (assessed only by those with the training and authority to make a diagnosis), and time of resolution/stabilization of the event.

Any medical condition that is present prior to Baseline Assessment will be considered as pre-existing or baseline and not reported as an AE. However, if the study participant’s condition deteriorates at any time during the study, and is possibly related to study intervention, it will be recorded as an AE.

Changes in the severity of an AE possibly related to study intervention will be documented to allow an assessment of the duration of the event at each level of severity to be performed. AEs characterized as intermittent require documentation of onset and duration of each episode.

Site PIs will record all reportable events consistent with the University of Cincinnati Human Research Protection Program Policy 11.02.

8.3.5 ADVERSE EVENT REPORTING

All reporting is done in accordance with StrokeNet Standard Operating Procedures for Safety Monitoring and Reporting as outlined in the administrative documents available on the website (<https://www.nihstrokenet.org/docs/default-source/default-document-library/adm13-safety-monitoring-and->

reporting-12-19-16.pdf?sfvrsn=0). Clinical sites report all SAEs and any AEs that have a reasonable possibility of being related to the intervention into WebDCU™. These events are coded using MedDRA. Sites are required to report SAEs within 24 hours and non-serious AEs within 5 days of their awareness of the event.

8.3.6 SERIOUS ADVERSE EVENT REPORTING

All SAEs are required to be reported in WebDCU™ within 24 hours of the study site being made aware of the occurrence of the SAE. The local site investigators are required to provide relevant information such as description of the SAE, date/time of onset and resolution, severity and seriousness, action taken, and suspected relationship to the study intervention. Reporting of SAEs will trigger notification of the event to the Project Manager (PM). After reviewing the SAE for completeness and accuracy, the PM will forward the SAE to the IMSM who will conduct an independent review of each SAE to determine its relationship to the study intervention along with other elements. The IMSM will then enter an opinion into WebDCU™ as to whether the SAE is, in fact, serious, unexpected, and related to the study intervention. After the submission of the initial SAE Report, the site investigator at the corresponding clinical site will be responsible for obtaining follow-up information about the event and reporting it in WebDCU™.

8.3.7 REPORTING EVENTS TO PARTICIPANTS

As part of the consent process we commit to informing parents if there are incidental findings from previous participants (including from other clinical sites) or findings that occur as a result of interim data analyses if these findings might have an impact upon allowing their child to participate. We will not and cannot ethically discuss specific events regarding any one participant but will indicate to any enrolled parents or future parents considering providing permission to participate that there have been one or some events beyond those currently identified as risks in the consent document approved by the CIRB. If this occurred, we would notify the CIRB about the method and wording of such notification to parents.

8.3.8 REPORTING OF PREGNANCY AND EVENTS OF SPECIAL INTEREST

Not Applicable

8.4 UNANTICIPATED PROBLEMS

8.4.1 DEFINITION OF UNANTICIPATED PROBLEMS (UP)

The Office for Human Research Protections (OHRP) considers unanticipated problems involving risks to participants or others to include, in general, any incident, experience, or outcome that meets **all** of the following criteria:

- Unexpected in terms of nature, severity, or frequency given (a) the research procedures that are described in the protocol-related documents, such as the Institutional Review Board (IRB)-approved research protocol and informed consent document; and (b) the characteristics of the participant population being studied;
- Related or possibly related to participation in the research (“possibly related” means there is a reasonable possibility that the incident, experience, or outcome may have been caused by the procedures involved in the research); and
- Suggests that the research places participants or others at a greater risk of harm (including physical, psychological, economic, or social harm) than was previously known or recognized.

8.4.2 UNANTICIPATED PROBLEM REPORTING

The investigator will report unanticipated problems (UPs) to the CIRB complying with the University of Cincinnati Human Research Protection Program Policy 11.01. The UP report will include the following information:

- Protocol identifying information: protocol title and number, PI’s name, and the IRB project number;
- A detailed description of the event, incident, experience, or outcome;

- An explanation of the basis for determining that the event, incident, experience, or outcome represents an UP;
- A description of any changes to the protocol or other corrective actions that have been taken or are proposed in response to the UP.

To satisfy the requirement for prompt reporting, UPs will be reported using the following timeline:

- UPs that are serious adverse events (SAEs) will be reported to the IRB and to the DCC/study sponsor within 5-days of the investigator becoming aware of the event.
- Any other UP will be reported to the IRB and to the DCC/study sponsor within 7 days in accordance when the investigator becoming aware of the problem.
- All UPs should be reported to appropriate institutional officials (as required by an institution's written reporting procedures), the supporting agency head (or designee), and the Office for Human Research Protections (OHRP) within 7 days of the IRB's receipt of the report of the problem from the investigator.

8.4.3 REPORTING UNANTICIPATED PROBLEMS TO PARTICIPANTS

All unanticipated problems will be reported as soon as possible (usually within 24-48 hours) to the child's parents in the event that the parents were not already of this. This may include a written description of the event and how the event will be followed up on. We will invite questions by parents and view this as an opportunity for discussion about any unanticipated events. The reporting and the resolution associated with the event will be documented in the study's history and, when applicable, in the individual subject's file.

9 STATISTICAL CONSIDERATIONS

9.1 STATISTICAL HYPOTHESES

1. Primary Aim: Determine the efficacy of I-ACQUIRE at 2 dosage levels compared to U&CT to increase upper extremity skills on the hemiparetic side. The primary efficacy outcome is a gain and retention of ≥ 7 new skills on the Emerging Behaviors Scale (EBS) at the end of the 4-wk treatment and 6 mos. later.

Hypothesis 1A: The 3 groups will differ significantly in the proportion of infants meeting primary efficacy criteria.
Hypothesis 1B: Both the Moderate Dose and High Dose I-ACQUIRE groups will have significantly higher proportions of infants meeting the primary efficacy criteria compared to U&CT.

Hypothesis 1C: The High Dose compared to Moderate Dose I-ACQUIRE group will have a significantly higher proportion of infants meeting the primary efficacy criteria.

Additional sensitivity analyses using repeated EBS scores (from 0 – 30) will explore specific aspects of treatment outcome and maintenance (e.g., differential magnitude of EBS changes across treatment groups) in relationship to predictor variables (e.g., stroke CNS damage coded from MRI scans, family engagement levels).

2. Secondary Aim: Determine the efficacy of I-ACQUIRE at 2 dosage levels compared to U&CT to improve use of the hemiparetic upper extremity in bimanual activities. The secondary efficacy outcome is the Mini Assisting Hand Assessment score at the end of 4-wk treatment and 6 mos. later.

Hypothesis 2A: The 3 groups will differ significantly in mean Mini AHAs at end of treatment and 6 mos later.

Hypothesis 2B: Both the Moderate Dose and High Dose I-ACQUIRE groups will have significantly higher mean Mini AHAs compared to U&CT at the end of treatment and 6 mos later.

Hypothesis 2C: High Dose compared to Moderate Dose I-ACQUIRE will have significantly higher Mini AHAs at end of treatment and 6 mos later.

3. Exploratory Aim: Explore the association between I-ACQUIRE treatment at Moderate and High Doses and gross motor development and cognition (i.e., cross-domain effects of treatment).

3A. Evidence-informed prediction for motor development: Both Moderate and High Doses of I-ACQUIRE will have higher mean gains in Gross Motor skills compared to U&CT at end of treatment and 6 mos later.

3B. Theory-informed prediction about cognition: High Dose I-ACQUIRE will be associated with larger mean gains in Cognition (Bayley-4) than Moderate Dose I-ACQUIRE and U&CT at 6 mos post-treatment.

9.2 SAMPLE SIZE DETERMINATION

The proposed minimal clinically meaningful threshold on the primary efficacy is a gain of 7 points after receiving High Dose I-ACQUIRE. We estimate 70% of children in the High Dose group will meet the primary efficacy outcome of ≥ 7 new EBS skills threshold at both post-treatment assessments. We further project that only 40% of the children in the Moderate Dose group will show primary efficacy, because we anticipate higher levels of decline over the 6-mth post-treatment period compared to those in the High Dose group. That is, we predict the new EBS skills at end of treatment will be less permanently established for subjects in the Moderate compared to High Dose group. Thus, to detect a minimal clinically meaningful difference in the primary efficacy outcome between the High and Moderate Dose groups with a two-sided type I error rate of 5% and 90% power, we would need a final randomized sample of $N=57$ subjects in each of the 3 groups. The sample size further inflates the required sample size to ensure adequate power after accounting for up to 15% of subjects lost to follow-up or missing outcome data using an inflation rate of 1.39¹⁰⁹.

We have limited data about precise EBS changes in children with PAIS receiving U&CT; thus, we relied on U&CT changes from 2 – 6 yr olds and from our clinical database. We estimate up to 15% of U&CT children may meet criteria for the primary outcome, because more families and therapists know about evidence supporting high therapy dosages and CIMT, and thus more U&CT children may be obtaining more effective therapy than in the past (when systematic reviews were conducted and published about many forms of U&CT). We have >80% power to detect a clinically significant treatment difference between either the Moderate Dose or High Dose I-ACQUIRE group and U&CT for any active treatment effect with $\geq 40\%$ of children with favorable outcomes. Finally, although the trial is specifically powered to detect differences in the primary outcome, given the total sample size of $N=240$ and a 5% type I error rate, the secondary and exploratory endpoints have $\geq 80\%$ power to detect pairwise differences in mean change as small as 5 units when the standard deviation is 10. Further note that power and sample size calculations use the conservative assumption of single-time point models and unadjusted analyses; in general, covariate-adjusted repeated measures models will have increased power to detect differences.

9.3 POPULATIONS FOR ANALYSES

Modified Intent to Treat (mITT) Sample

All efficacy analyses (primary, secondary, and exploratory) will be conducted using a modified ITT (mITT) sample. That is, the evaluable sample includes all randomized subjects who continue to meet the inclusion/exclusion criteria at the time of Baseline Assessment and who complete the Baseline Assessments prior to treatment initiation, notwithstanding whether or not the subjects completed the study treatment protocol for their group. A sensitivity analysis will consider differences between the mITT sample and a traditional ITT sample, which is inclusive of the mITT sample but also analyzes all subjects who are randomized but withdraw, are lost to follow-up, or no longer meet inclusion criteria prior to the time when a baseline assessment would have occurred.

As Treated Sample.

Sensitivity analyses will use the as treated sample when specified. That is, the evaluable sample includes all randomized subjects, regardless of whether or not the subjects completed the treatment as planned. In contrast to the mITT sample which categorizes treatment by randomly assigned group, the As Treated Sample analyses will consider the dose of treatment defined as the actual number of treatment sessions as well as total hours received (e.g., a child who is perfectly compliant in the Moderate Dose or High Dose I-ACQUIRE is expected to get 60 or and 120 hours of I-ACQUIRE treatment respectively).

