1 PROTOCOL SUMMARY

1.1 SYNOPSIS

Title:	Perinatal Arterial Stroke: A Multi-site RCT of Intensive Infant Rehabilitation (I-ACQUIRE)
Study Description:	This is a Phase III clinical trial to compare the efficacy of two dosages of a new infant rehabilitation protocol - I-ACQUIRE - to usual and customary forms of infant rehabilitation in infants who experienced Perinatal Arterial Ischemic Stroke (PAIS).
Objectives:	
1) Determine the efficacy of I-ACQUIRE at 2 dosage levels compared to Usual and Customary Treatment (U&CT) to increase upper extremity skills on the hemiparetic side.2) To determine the efficacy of I-ACQUIRE at 2 dosage levels compared to U&CT to improve use of the hemiparetic upper extremity in bimanual activities.3) To explore the association between I-ACQUIRE treatment at Moderate and High Doses and gross motor development and cognition (i.e., cross domain effects of treatment)
Endpoints:	End of Treatment and 6 mos. Post-Treatment
Study Population:	Infants with Perinatal Arterial Ischemic Stroke between 8 and 36 mos. of age.
Phase:	Phase III Clinical Trial
Description of Sites/Facilities Enrolling Participants:	10 are NINDS StrokeNet sites, 2 are outside clinical sites
Description of Study Intervention:	I-ACQUIRE is an innovative form of intensive pediatric rehabilitation that includes core elements of pediatric Constraint-Induced Movement Therapy with supplement components of bimanual and whole body motor activities and a parent home program, delivered in natural settings. Previous smaller-scale trials showed high safety, acceptability, treatment compliance, and both statistically and clinically significant benefits.
Study Duration:	Study period is 5 years with enrollment open approximately 6 months into Year 1 through Year 5.
Participant Duration:	Participants will be involved for a minimum of 7 months and up to 13 months (depending on scheduling of the treatment month).

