4 STUDY DESIGN

4.1 OVERALL DESIGN

The proposed study is a Phase III trial powered to determine efficacy of two different doses of I-ACQUIRE for children 8 to 24 months old with PAIS and hemiparesis. The design is a prospective RCT in which 240 children will be randomly assigned to one of 3 treatment groups (N=80 per group): 1) Moderate Dose I-ACQUIRE (3 hrs/day, 5 day/wk X 4 wks), 2) High Dose I-ACQUIRE (6hrs/day, 5 days/wk X 4 wks), or 3) Usual and Customary Treatment (U&CT). I-ACQUIRE will be delivered by protocol-trained therapists and monitored weekly for dosage and treatment fidelity; U&CT will be provided by community therapists with dosage and approaches documented weekly. All primary and secondary efficacy outcomes rely on blinded assessments at baseline, end of treatment, and 6 mos post-treatment. Exploratory outcomes and supplemental clinical measures may provide valuable additional data about development and health in this sample of children with PAIS.

There will be a second phase of the I-ACQUIRE Study for the children who had been randomly assigned to Group 3 (Usual and Customary Treatment). Their parent(s) may choose to enroll (via a new IRB-approved consent process) to have their child randomly assigned to receive either the Moderate or High Dose I-ACQUIRE treatment. This will occur after the 6-mos Post-Treatment Assessment from the primary phase. Outcome data from this second or crossover phase of the study will not be used in the primary data analysis for this trial but will be available for exploratory and post hoc data analyses.

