6.3 MEASURES TO MINIMIZE BIAS: RANDOMIZATION AND BLINDING

Subjects will be randomized in a 1:1:1 fashion to U&CT, Moderate Dose I-ACQUIRE, or High Dose I-ACQUIRE using a restricted randomization algorithm which controls for within site treatment imbalances. If no imbalances exceed the tolerated threshold, the patient is randomized according to the specified allocation ratio (1:1:1) using a block urn design. If an unacceptable level of imbalance exists, the algorithm will determine whether the current allocation ratio improves or exacerbates the current imbalance and adjust the ratio accordingly. The detailed randomization scheme and source codes will be provided in the Randomization Plan document. Note: for general understanding, the randomization process will be described in the consent document for parents as having an equally fair chance of being assigned to one of the 3 treatment groups.

Upon confirmation of eligibility and obtaining parental permission to participate, study coordinators will log into the WebDCU™ study database and receive the computer-generated randomization assignment. Local Site Coordinators will notify families promptly to schedule baseline assessments and designate the treatment month.

It is not possible to blind the family or the treatment team; however, no treating therapist will conduct assessments for primary and secondary outcomes, and none of the blinded assessors will work in the same setting as treatment staff. In addition, the primary and secondary outcomes will be coded by staff at the Central Assessment Core at The Ohio State University, remote from the clinical site and treatment implementation core. Assessment Core research staff will be blinded to treatment and the videos will be randomly sorted so that central coders cannot know whether a video is the baseline or one of the follow-up assessments. Parents also are reminded before each assessment session not to discuss their child's treatment with the assessor.

For assessments completed by the local blinded assessor, a second blinded scoring will be calculated by the central blinded assessment team if the local assessor has indicated that he or she possibly has become unblinded. Only blinded scores will be used in the primary analysis, but sensitivity analyses will compare the local and central scores to assess for any potential differences due to the unblinding.

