9.4.2 ANALYSIS OF THE PRIMARY EFFICACY ENDPOINT(S)

The primary analysis (Aim 1) will use a modified intent-to-treat (mITT) study sample defined as those subjects who attend the baseline visit and continue to meet eligibility. This approach will permit exclusion of subjects who are randomized, but then drop out prior to any baseline data being collected, due to changes in eligibility or family circumstances that preclude any study participation. The sample size for analysis will be 240 subjects who meet the mITT definition.

Missing outcomes will be imputed as unfavorable, which is a conservative but reasonable approach given minimal (<5%) missing data. If the amount of missingness is unexpectedly high, e.g. >5%, then missing primary outcome data will be imputed via standard multiple imputation methods (i.e., via logistic regression model predicting outcome based on pertinent baseline and treatment data). The primary analysis will test the sequence of null hypotheses using fitted estimates from a logistic regression model, where the dependent variable is the dichotomized indicator of a favorable outcome, ≥ 7 new EBS skills above baseline at the end of 4-wk treatment and 6 mos post-treatment. An interim analysis for futility is planned after $N=120$ ($N=$ approximately 40/group) subjects complete the 6-month post-treatment visit using a non-binding O'Brien and Fleming type stopping boundary. Sensitivity analyses of the primary analysis will also consider the impact of distribution-based methods, using a generalized linear mixed-effects repeated measures model where change in EBS is modeled as continuous and the model is adjusted for baseline EBS score, treatment group, study visit (4 weeks or 6 months), and an interaction for treatment group and visit. Subgroup analyses will evaluate the impact of race/ethnicity, gender, neuroimaging biomarkers of injury, therapy fidelity, and parental involvement. The impact of U&CT dose variability will also be assessed in a model where the categorical indicator for treatment group will be replaced by a continuous covariate measuring total hours of therapy received and a categorical indicator for type of therapy.

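### The arm is assigned openly before baseline, and the primary mITT set then drops children who leave or lose eligibility, so exclusions can depend on arm; 240 is also used both as the number randomized and as the mITT number

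*Protocol*

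**What the plan says.** **Order of events.** Under Protocol 6.3, after eligibility and parental permission are confirmed, "study coordinators will log into the WebDCU™ study database and receive the computer-generated randomization assignment". Next, "Local Site Coordinators will notify families promptly to schedule baseline assessments and designate the treatment month". The same section states that "It is not possible to blind the family or the treatment team". Section 10.1.1.2 has parents reconfirm their willingness at the first baseline assessment, which comes after assignment.

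**Primary set.** Section 9.3 defines the mITT sample as "all randomized subjects who continue to meet the inclusion/exclusion criteria at the time of Baseline Assessment and who complete the Baseline Assessments" before treatment starts. Section 9.4.2 gives the purpose: to leave out randomized children who drop out before baseline because eligibility or family circumstances changed. A comparison with a traditional ITT sample that keeps these children is planned as a sensitivity analysis (9.3).

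**Time available.** The Synopsis (1.1) says: "Participants will be involved for a minimum of 7 months and up to 13 months (depending on scheduling of the treatment month").

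**Numbers.** Section 4.1 says "240 children will be randomly assigned to one of 3 treatment groups (N=80 per group"). Section 9.4.2 says "The sample size for analysis will be 240 subjects who meet the mITT definition". Section 5.5 likewise counts 240 families who complete baseline.

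**The concern.** Membership of the primary set is settled after an open assignment. Some routes out lie in the family's hands: withdrawing, not attending baseline, obtaining botulinum toxin or enough outside CIMT to meet an exclusion in 5.2, or no longer being willing to do the home component required by 5.1. If these happen at different rates, or in different kinds of children, by arm, the groups compared are no longer those that randomization formed. The confirmatory tests are run on this set, and the set that keeps every randomized child has only a supporting role.

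Separately, 240 cannot be both the number randomized and the number left after mITT exclusions, unless no child is excluded.

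**Working it through.** **1. The plan's own sample size.** Section 9.2 uses 70% against 40%, two-sided 5% and 90% power. The pooled two-proportion formula gives 56 per group; the plan states 57. Then 57 x 1.39 = 79.2, rounded up to 80, and 3 x 80 = 240. The factor matches 1/(1 - 0.15)^2 = 1.384. The 15% is described as covering loss to follow-up or missing outcomes; exclusions before or at baseline are not mentioned.

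**2. Time between assignment and baseline.** One treatment month plus six months of follow-up is 7 months, so the stated range leaves 13 - 7 = 6 months of slack. Some of this may be visit windows: 11.1 mentions up to 2 months' delay at the six-month visit, which would leave 13 - 7 - 2 = 4. Some may fall before assignment or between baseline and treatment, where it does not affect mITT membership. A gap is certain; its length is not stated.

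**3. Which exclusions can depend on arm.**

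| Route out of the mITT set | Can the arm influence it? |
|---|---|
| Diagnosis, MRI | No: fixed before assignment |
| Baseline EBS above 24 | Least likely: scored centrally, blind to arm |
| Withdrawal or missed baseline | Yes |
| Intervening CIMT or botulinum toxin | Yes |
| Parent no longer willing to do the home component | Yes |

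**4. Illustrative shift in one arm.** If a share d leaves and would have succeeded at rate s, the rate among stayers is (p - d*s)/(1 - d). Take p = 0.15 for U&CT (9.2). Both d and s are assumptions.

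- d = 0.10, s = 0.40: (0.15 - 0.04)/0.90 = 12.2%
- d = 0.20, s = 0.40: (0.15 - 0.08)/0.80 = 8.75%
- d = 0.10, s = 0.05: (0.15 - 0.005)/0.90 = 16.1%
- d = 0.20, s = 0.05: (0.15 - 0.01)/0.80 = 17.5%

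The sign depends on who leaves.

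**5. Illustrative false-positive rate.** Assume no true difference, loss in U&CT only, 80 per arm analysed, and a two-sided 5% normal-approximation test of one pair.

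| Common rate | Leavers' rate | d = 5% | 10% | 15% | 20% |
|---|---|---|---|---|---|
| 15% | 30% | 5.2% | about 6% | 7.7% | 10.8% |
| 15% | 0% | 5.2% | about 6% | 7.4% | 9.7% |
| 40% | 80% | about 5.9% | 8.9% | 15.2% | 26.2% |
| 40% | 0% | 5.8% | 8.8% | 14.6% | 24.5% |

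In the 0% rows the shift runs against I-ACQUIRE.

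**6. What the ITT comparison would show.** A child who leaves before baseline has no baseline EBS, so no gain can be computed and the result rests on imputation. Section 9.4.2 counts missing outcomes as unfavorable unless missingness exceeds about 5%. Suppose that rule carries over to the ITT set.

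- With d = 0.10 in U&CT only, about 0.10/3 = 3.3% are missing overall. For s = 0.40 the ITT rate is 0.90 x 0.122 = 11%, further from the true 15% than the mITT's 12.2%.
- With d = 0.20, about 6.7% are missing, so multiple imputation applies. Without a baseline EBS it borrows mainly from stayers and returns roughly the mITT value.

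**7. Range over the unknown success rates.** The ITT difference is (1 - dT)rT + dT*sT - (1 - dU)rU - dU*sU, where r is the observed mITT rate, s the rate among excluded children, and T and U denote Moderate Dose and U&CT. Let each s run from 0 to 1, with rT = 0.40 and rU = 0.15.

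- 5% excluded in both arms: 0.95 x 0.25 = 0.2375, plus or minus 0.05, so 18.75 to 28.75 points
- 10% excluded in both arms: 0.90 x 0.25 = 0.225, plus or minus 0.10, so 12.5 to 32.5 points

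**8. The two uses of 240.** At 5-10% exclusion (assumed), 240 randomized leaves 228-216 in the mITT set, and 240 in the mITT set needs 240/0.95 = 253 to 240/0.90 = 267 randomized.

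**The case against.** A reader might infer that the plan favors I-ACQUIRE because disappointed U&CT families leave for CIMT elsewhere. The documents do not support that direction. U&CT families may receive I-ACQUIRE after the six-month assessment (4.1, 6.1.2), agree not to change their usual care (8.3.3.2), and are barred from botulinum toxin and other CIMT until then (5.2). Outside CIMT seldom qualified as evidence-based in the team's experience (2.2), and lower doses do not exclude a child (5.2). I-ACQUIRE families have their own reasons to leave: 3 or 6 hours of therapy a day, a continuously worn cast and a home program (6.1.1). All of this stands, and it leaves the direction open.

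The planned differences are also large: 25 and 55 points from U&CT, and 30 between doses. The High against Moderate contrast, on which the sample size rests, does not involve U&CT at all, although losses could differ between the two doses as well. If the planned effects are real, modest exclusion would not overturn them in point estimate (step 7).

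The mITT choice is a reasoned, documented amendment (10.4), and the ITT comparison is planned. Section 6.3 says families are contacted promptly, and it does not expressly say that they learn the arm at that contact; this is inferred from the open design and from setting the treatment month then.

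None of this removes the problem of order. The ban on outside treatment does not protect the analysis, because a family that breaks it before baseline removes its child from the primary set. Nor does it follow that simply making ITT primary would cure the problem: step 6 shows that it can move the estimate further from the truth.

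**Conclusion.** The point holds as one of design. The primary comparison conditions on events after an open assignment, and several of those events can depend on arm. The planned ITT sensitivity analysis mitigates this only in part.

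The direction and size of any bias cannot be determined from the protocol. The figures in steps 4 and 5 rest on assumed, one-sided loss of 5-20% and assumed success rates among leavers. They show that the effect could be negligible or material, in either direction, and they are not estimates for this trial. A reader should not take a 3 to 6 point inflation of the dose effects as established.

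The conflict over 240 is definite. Sections 5.5 and 9.4.2 agree that 240 counts children who complete baseline or meet the mITT definition, and 4.1 is the outlier. It is mainly a wording correction, but it determines how many children must be randomized.

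**What to change.** - **New enrolments.** Amend 6.3 so that WebDCU releases the assignment only after the baseline visit is complete and eligibility other than the EBS limit is reconfirmed. The EBS exclusion can stay after randomization because it is scored centrally and blind to arm. Waiting for that score would be unnecessary, and it would strain the masking in 6.3, under which central coders cannot tell baseline from follow-up videos. Cost: an amendment, and therapist and treatment-month scheduling must follow baseline.
- **Children already randomized.** Report exclusions before or at baseline by arm and by reason. Run the planned ITT comparison over a range of success rates for the excluded children, set separately by arm as in step 7, and not only with missing counted as unfavorable. Cost: a few extra tables and wider stated uncertainty.
- **Numbers.** Correct 4.1. Either state that 240 is the mITT target and give a larger number to randomize (about 253-267 at an assumed 5-10% exclusion), or keep 240 randomized and state the smaller mITT number (228-216) in 5.5 and 9.4.2. The first option costs 13-27 more randomizations. The second lowers the analysed number: 216/3 = 72 per group, and 72/1.39 = 51.8 against the 57 required in 9.2.
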